- This study is established as a non-inferiority study, such that the research hypothesis is that green / violet dual-diode therapy with the Erchonia® GVL is either equivalent to or superior to red / violet dual-diode therapy with the Erchonia® EVRL in effecting a clinically meaningful temporary reduction in neck and shoulder pain of musculoskeletal origin when compared with the data attained from the red / violet dual-diode Erchonia® EVRL clinical trial conducted in 2019 (comparative reference study) whose results successfully supported 510(k) clearance of K191257, given that the application and evaluation of the Erchonia® GVL in the current study is intended to support clearance of the Erchonia® GVL for the identical indication as the Erchonia® EVRL.

Therefore:

- The individual subject success criteria in this clinical study as specified above is selected to be identical to that of the comparative reference study.
- The overall study success criteria in this clinical study is determined based on the actual proportion of individual subject successes attained during the comparative reference trial of 75%. The $\pm 5\%$ is the selected equivalence margin (δ), the maximally clinically acceptable difference for which the range of values (70% to 80%) for which the efficacies are “close enough” to be considered equivalent.
- Non-inferiority is established to be attained if the proportion of study subjects in this GVL study who meet the individual subject success criteria is no more than 5% less than the proportion of study subjects in the comparative reference EVRL study who met the same individual success criteria, i.e., no less than 70%.

This strategy is the identical strategy employed in the clinical study for the Erchonia® EVRL in red / violet dual-diode mode whose results supported FDA clearance of K191257 based on the same equivalency criteria to the comparative reference group of the active treatment arm of the Erchonia® EVRL in red-diode only mode that had previously received FDA clearance under K012580 and K152196, for the identical indication.

Hypotheses

- *Null Hypothesis:* Treatment application of the Erchonia® GVL in simultaneous green / violet dual-diode mode is inferior to treatment application of the Erchonia® EVRL in simultaneous red / violet dual-diode mode in reducing neck and shoulder pain of musculoskeletal origin.

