- *Alternative Hypotheses:* Treatment application of the Erchonia® GVL in simultaneous green / violet dual-diode mode is NOT inferior to treatment application of the Erchonia® EVRL in simultaneous red / violet dual-diode mode only in reducing neck and shoulder pain of musculoskeletal origin.

Evaluation Time Point

Study endpoint evaluation is established as immediately (within 3 minutes) following the study single procedure administration. Study success analysis is established at study endpoint relative to baseline.

The study endpoint evaluation for this study was established to be identical to that in the reference comparative study.

Populations Examined

Primary analysis of efficacy will be according to intent to treat (ITT) analysis (including all enrolled subjects) supported by per protocol (PP) analysis (including only subjects who completed the study according to the full protocol). Non-inferiority will be established if both the ITT and PP analyses agree.

Handling of Missing Data

Missing data for the ITT population will be handled through Last Observation Carried Forward (LOCF): by carrying forward the last recorded observation to fill in the subsequent missing value

PRIMARY EFFICACY OUTCOME STATISTICAL EVALUATION

Primary efficacy outcome success will be determined as follows:

Proportion of Successes

- The percentage of individual subject successes in this clinical study will be calculated according to the pre-specified criteria of a decrease in VAS pain ratings of 30% or greater from baseline to endpoint evaluation.
- **Primary study success will be considered met, i.e., non-inferiority will be established, according to the pre-specified overall study success criteria, if this proportion is not less than 70%.**

Comparison of Proportions

A comparison of proportions test will be performed to evaluate if the two success proportions (GVL vs. EVRL) are equivalent to support the conclusion of the proportions of successes analysis. Significance levels will be considered at the $p<0.05$ level.

Change Scores

- T-test analysis of the difference in the mean change in VAS levels from baseline to endpoint between the dual-diode and red only diode treatment administration groups. Significance levels will be considered at the p<0.05 level.

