- A t-test for two independent sample will be performed to evaluate the significance of the difference in the mean change in VAS pain scores from baseline to endpoint evaluation between the two study groups (GVL vs EVRL) to evaluate for equivalency to support the support the conclusion of the proportion of successes evaluation. Significance levels will be considered at the p<0.05 level.

SECONDARY EVALUATIONS

The following secondary evaluations will be performed on the GVL study data set. As no claims are intended to be made based on the secondary measures, the findings are presented through descriptive analysis and qualitative trending only, without evaluation for or claims of statistical significance.

- Change in mean VAS ratings across study duration: all study evaluation points (baseline, endpoint, 24 hours and 48 hours post-procedure).
- Change in linear ROM measurements across respective study evaluation points at study baseline and endpoint.
- Subject satisfaction with study outcome ratings across study duration.

INDIVIDUAL TEST SITES

Results will be presented by individual test site for comparison.

INDIVIDUAL SUBJECT RESULTS

Individual subject results for study outcome measures will also be presented.

SAFETY ANALYSES

Safety analyses will be based on all enrolled subjects and will be assessed by evaluating and comparing frequency and incidence of observed and/or reported adverse events between subjects in the GVL and the EVRL studies. A chi-square test with a continuity correction will be performed to compare the percentage of subjects who had adverse events between the two subject groups.

INFORMED CONSENT

- Informed consent will be an agreement between the individual investigator and each subject, having the capacity to understand and make an informed decision. Consent will be obtained prior to each potential subject's participation in this clinical study.
- Each subject participating in this clinical study will be made aware of the fact that his or her participation involves research and the intent of the research, the expected duration of his or her participation and a description of the procedures that will be followed.
- Each subject will be made aware of the reasonably expected benefits he or she might receive, as well as any risks or potential discomfort that are involved.
- Each subject will also be made aware of alternative treatments available to him or her.

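### The supporting GVL vs EVRL tests are meant to show equivalence at p<0.05 without stating the 5-point margin; read as a difference test, the proportions test cannot contradict a 70% pass

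*Combined protocol and SAP*

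**What the plan says.** Under Hypotheses, the null is that GVL is inferior to EVRL. Justification for Study Success Criteria sets a margin of 5 percentage points around the EVRL rate of 75%, described as "the maximally clinically acceptable difference for which the range of values (70% to 80"%). Non-inferiority holds if the GVL proportion "is no more than 5% less than the proportion of study subjects in the comparative reference EVRL study". Under Proportion of Successes this becomes one rule on the observed rate: success "if this proportion is not less than 70"%. Populations Examined adds: "Non-inferiority will be established if both the ITT and PP analyses agree".

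The supporting efficacy analyses, all at p<0.05, are:

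- **Comparison of Proportions:** "A comparison of proportions test will be performed to evaluate if the two success proportions (GVL vs. EVRL) are equivalent", in support of the 70% result.
- **Change Scores, first bullet:** a t-test on mean VAS change "between the dual-diode and red only diode treatment administration groups".
- **Change Scores, second bullet:** a two-sample t-test of GVL against EVRL "to evaluate the significance of the difference in the mean change in VAS pain scores from baseline to endpoint evaluation", and its purpose is "to evaluate for equivalency to support the support the conclusion of the proportion of successes evaluation".

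No margin, confidence interval or two one-sided tests procedure is attached to any of them. No margin on the VAS scale appears anywhere. The plan does not say how a p-value on either side of 0.05 would be read.

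**The concern.** A difference test has a null of no difference. Failing to reject it does not reject the plan's own null of inferiority, and in a small study it is the expected result whether or not the devices differ. For VAS change, the wording leaves no doubt that a difference test is being used to show equivalence. For the proportions, a difference test is the natural reading. A margin-based test is possible but not stated, and the two readings can give opposite answers.

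These are the only formal efficacy comparisons of GVL with EVRL, and the results are meant for a 510(k) submission. On the natural reading, the proportions test cannot warn of inferiority once the 70% rule is met, but a report could cite it as a second confirmation. It can be significant only in GVL's favour. A test of whether the rates are equivalent would then appear to fail, although Expected Results anticipates equivalent or superior results.

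The first Change Scores bullet does not fit this study at all: GVL (green/violet) and the EVRL comparator (red/violet) are both dual-diode, and there is no red-only group.

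**Working it through.** **Inputs.** GVL n = 43 (Sample Size). EVRL rate 75% and margin 5 points (Justification for Study Success Criteria). The EVRL sample size is not given; Rationale for Sample Size says only that 43 matches the number that study intended to enrol. No count out of 43 equals 75% (32/43 = 74.4%, 33/43 = 76.7%), so every EVRL count below is an assumption.

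**The plan's own figure.** 75% - 5% = 70%, as stated. Since 30/43 = 69.8% fails, the smallest pass is 31/43 = 72.1%.

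**Can a passing GVL result be significantly lower?** Pooled z-test, z = (p1 - p2) / sqrt[p(1 - p)(1/n1 + 1/n2)]. For 31/43 against 32/43, p = 63/86 = 0.7326, the standard error is sqrt(0.7326 × 0.2674 × 2/43) = 0.0955, z = -0.0233/0.0955 = -0.24, and two-sided p = 0.81. Other assumed references:

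| EVRL (assumed) | p for GVL 31/43 |
|---|---|
| 32/43 | 0.81 |
| 33/43 | 0.62 |
| 33/44 | 0.76 |
| 30/40 | 0.76 |
| 45/60 | 0.74 |

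A smaller PP set does not change this: 28/40 (exactly 70%) against 33/44 gives p = 0.61. Over GVL n of 30 to 43 (smallest passing count) and EVRL n of 30 to 120 at 74.5% to 75.5%, the smallest p for a passing shortfall is 0.50. Allowing EVRL rates up to 77% lowers it to 0.38. A significant shortfall at 43 per group needs GVL at or below 23/43 against 32/43, or 24/43 against 33/43, a gap of about 21 points.

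**What the same data say about the margin.** Newcombe lower limit = d - sqrt[(p1 - l1)² + (u2 - p2)²], where l and u are Wilson limits. For 31/43 (57.3% to 83.3%) and 32/43 (59.8% to 85.1%), d = -2.3 points and the lower limit is -2.3 - sqrt(14.8² + 10.7²) = -20.5. The upper limit is +16.1. The Wald interval is -21.0 to +16.4.

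**Where the two readings disagree** (EVRL 32/43):

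| GVL | p, difference test | Newcombe lower limit (points) |
|---|---|---|
| 31/43 | 0.81 | -20.5 |
| 37/43 | 0.18 | -5.4 |
| 38/43 | 0.096 | -2.7 |
| 39/43 | 0.047 | 0.0 |

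From 31 to 37 successes the difference test is non-significant while the lower limit is below -5. The binomial probability of that range is 45%, 71% or 81% if GVL's true rate is 70%, 75% or 80%. From 39/43 the test is significant in GVL's favour; 40/43 is needed against 33/43 or 33/44.

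**VAS t-test.** With 43 per group (84 df), the largest non-significant difference is t(0.975) × sqrt(2/43) = 1.989 × 0.2157 = 0.429 SD. The plan gives no SD. For assumed SDs of 15, 20 and 25 mm this is 6.4, 8.6 and 10.7 mm.

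**The case against.** The strongest reply is that nothing is decided by these tests. Only the 70% rule declares success; the comparisons are supportive, and the plan never says that a non-significant p will be read as confirmation. That stands, and it limits the harm to what the report may claim.

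Second, the plan defines equivalence by its 5-point margin, so a margin-based proportions test may be intended. That is possible, but nothing in the text specifies one. The cannot-contradict result applies only to the difference-test reading. The defence is not available for the t-test.

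Third, a shortfall of at most 5 points presumes a reference of exactly 75%. Against 33/43, a PP result of 28/40 passes with a 6.7-point shortfall. This is correct, but p is then 0.49 and the conclusion is unchanged.

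Fourth, the wide interval and low chance of clearing the margin come from the sample size and the point-estimate rule, which are separate problems. That is also right; those figures show why the tests are uninformative and should not be counted again here.

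Fifth, the red-only bullet looks like carried-over wording and cannot be run with the two data sets supplied. It still needs to be reconciled.

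**Conclusion.** The concern holds and should be fixed. The VAS t-test is a difference test used to show equivalence, with no margin. The proportions test is unspecified, and on its natural reading it cannot contradict a 70% pass at this size: p is 0.62 or higher for 31/43 against each reference tabulated, and no passing shortfall comes near 0.05 for EVRL rates up to 77%. Against 32/43, the difference and margin readings disagree for GVL counts of 31 to 37. The t-test can overlook a deficit of up to 0.43 SD.

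The proportion figures rest on assumed EVRL counts, and the mm figures on assumed SDs. The claim that a shortfall cannot be significant concerns the proportions test only; the t-test could still be significant after a 70% pass. Success itself does not depend on any of these tests.

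**What to change.** Replace the p<0.05 efficacy criteria with the GVL minus EVRL estimate and a two-sided 95% CI, in both the ITT and PP sets.

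- **Proportions:** name the interval method (for example Newcombe) and compare the lower limit with -5 points. If it is below -5 in either set, the report states that the between-study comparison does not confirm the margin.
- **VAS change:** compare the CI with a margin in mm that the sponsor fixes before the data are analysed. The EVRL results are already known, so the basis for that margin should be written down.
- **Change Scores:** reconcile the first bullet with the second so that one GVL vs EVRL comparison remains.
- **Add a sentence:** a p-value of 0.05 or more from a difference test will not be read as support for equivalence or non-inferiority.

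This costs SAP wording and one margin to choose, with the same data and software and no new subjects. The real cost is a less favourable supporting claim. At equal rates of 32/43 the CI half-width is 1.96 × sqrt(2 × 0.744 × 0.256/43), about 18 points. If both true rates are 75%, the lower limit clears -5 about 8% of the time (2.6% with EVRL fixed at 32/43). GVL would need 38/43 against any of the five assumed references. The edit does not repair the 70% point-estimate rule or the sample size.

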There will be a single subject group in this study. All subjects will receive the active study procedure with the green and violet diodes of the Erchonia® GVL emitted simultaneously.

Comparative subject data for Erchonia® EVRL emitting the red and violet diodes simultaneously will be taken from the 2019 study whose results supported FDA market clearance for K191257.

BLINDING

As all subjects in this study will receive the active procedure administration with the Erchonia® GVL, neither subjects nor investigators will be blinded. The statistician analyzing the study results will however be blinded with respect to study success analysis. The data from this current GVL study and the retrospective data from the 2019 EVRL study will be deidentified and presented to the study statistician as 'Group A' and 'Group B'. The statistician will not be aware of which group – A or B – contains the current GVL study data and which contains the retrospective comparative EVRL study data.

RANDOMIZATION

As this study is a single treatment group study, randomization to procedure group is not applicable. Therefore, this is a non-randomized trial.

SUBJECTS

Subject Sample

Subjects will be males and females 18 years or older who present with chronic (30 consecutive days or longer) neck and/or shoulder pain diagnosed as being of musculoskeletal origin (osteoarthritis, chronic muscle spasm, cervical and thoracic spine sprain strain).

Sample Size

There will be 43 qualified subjects enrolled in this study.

Rationale for Sample Size

Sample size is determined to be identical to that intended to be enrolled in the comparative reference EVRL study.

Recruitment

Subjects may be recruited from among:

- (i) The Principal Investigator's/test site's pool of existing and new patients
- (ii) Referrals from other suitable medical clinics and professionals
- (iii) Subjects who respond to the following recruitment materials:

a) Flyer

WANTED

**ADULTS WITH NECK AND SHOULDER PAIN
ONGOING FOR THE LAST 30 DAYS FOR A
CLINICAL STUDY OF THE EFFECTS OF
LOW LEVEL LASER LIGHT ON
REDUCING NECK AND SHOULDER PAIN**

**THIS STUDY INVOLVES A SINGLE
LASER LIGHT PROCEDURE
WITH THE ERCHONIA® GVL LASER
AT THE TEST SITE**

FOR MORE INFORMATION PLEASE CONTACT:

<PI name>
<test site name & location>
<phone # and/or e-mail>

b) Newspaper Ad

Neck and Shoulder Pain Research Study

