- (i) Over the counter and prescription medications currently used to relieve neck/shoulder pain, including duration, dosage, and frequency of use
- (ii) Non-drug treatments/therapies (conventional, alternative, and experimental) currently used to relieve neck/shoulder pain, including duration and frequency or use/application
- (iii) Over the counter and prescription medications currently used, and therapies currently engaged in for any non-pain relief indication, including duration, dosage, and frequency of use

SUBJECT DEMOGRAPHICS: Age, gender, and ethnicity

OUTCOME ASSESSMENT TOOLS

VISUAL ANALOG SCALE (VAS) DEGREE OF PAIN RATING

Subjects will be asked to rate the overall degree of pain experienced in the neck / shoulder region on the following 0-100 mm (0 -10 cm) Visual Analog Pain Scale, by responding to the following question:

"Using the scale below, please mark with a cross (X) a SINGLE SPOT along the 0 to 100 line below that best shows how much pain you feel in your neck / shoulder right now. '0' means you feel no pain at all and '100' means you feel the worst pain imaginable. PLEASE MARK ONLY ONE SPOT. DO NOT THINK OF OR WRITE IN A NUMBER."

The Visual Analog Pain Scale (VAS) is one of the three most commonly used scales for assessing chronic pain. It is a simple scale that consists of a line anchored at one end by a label such as "NO PAIN" and at the other end "WORST POSSIBLE PAIN". The subject marks on the line the spot for the pain intensity, which is then measured.

Standard guidelines for effective use of the VAS that are followed in this clinical study are:

- i. The line should be 10, 15 or 20cm long, as other lengths are less reliable.
- ii. There should be a small vertical mark at each end, with numbers 0 and 100, and a verbal description.
- iii. The verbal description must be in absolute terms (e.g., worst pain imaginable);
- iv. The line itself should be clear of any markings and should be horizontal rather than vertical, for more reliable measurements.

Used in the above way, it has been shown that the VAS is a proper ratio scale. Like a thermometer, this means that its two ends are rooted, and a doubling of the score does accurately reflect a doubling of the pain. Consequently, sensitive t-tests and ANOVA methods can be used in the analysis, so that significant differences can be identified with relatively small sample sizes or small differences between groups.

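### The Change Scores t-test is asked to show equivalence but tests only for a difference, with no VAS margin, so it adds almost nothing to the 70% rule

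*Combined protocol and SAP*

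**What the plan says.** The Change Scores part of the SAP's Primary Efficacy Outcome Statistical Evaluation has two bullets.

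- The second is the operative one. A two-independent-sample t-test is "performed to evaluate the significance of the difference in the mean change in VAS pain scores from baseline to endpoint evaluation". Its purpose is given in the same sentence, as a comparison "between the two study groups (GVL vs EVRL) to evaluate for equivalency to support the support the conclusion of the proportion of successes evaluation". The test level is p<0.05. Sidedness, a margin in mm and a confidence-interval rule are not given.
- The first is a t-test of the same quantity "between the dual-diode and red only diode treatment administration groups", also at p<0.05.

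The planned data are described under Subject Group and Blinding: one green/violet GVL group, and red/violet EVRL data from 2019. "The data from this current GVL study and the retrospective data from the 2019 EVRL study will be deidentified" and handed to the statistician as Groups A and B. Both are dual-diode.

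The only margin is 5 percentage points on the responder proportion (Justification for Study Success Criteria). The 70% threshold comes from that margin and is "determined based on the actual proportion of individual subject successes attained during the comparative reference trial of 75" percent. Primary success is decided separately: the observed GVL proportion must not fall below 70%. The neighbouring Comparison of Proportions paragraph likewise asks whether the two proportions are equivalent, at p<0.05, in support of the same conclusion.

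On numbers, 43 subjects are to be enrolled: "Sample size is determined to be identical to that intended to be enrolled in the comparative reference EVRL study". No power, SD or effect size is given for the change-score test.

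**The concern.** The plan's null hypothesis is that GVL is inferior. The t-test's null is that the two means are equal. Rejecting equality shows a difference. Failing to reject it shows only that the data did not reveal one, and that happens more often as the sample shrinks. A test without a margin therefore cannot do the job assigned to it. The 5-point margin does not fill the gap, because it concerns the share of subjects with a 30% decrease and says nothing about an acceptable loss in mean mm.

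At stake is a sentence in the study report: whether VAS change may be said to support non-inferiority. The 70% rule compares one observed proportion with a fixed number. EVRL's observed 75% sets that number, but its sampling uncertainty enters the efficacy conclusion only through the supportive tests. Those tests should therefore show what the data can and cannot exclude.

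**Working it through.** **Plan's own figure.** There is no calculation to reproduce. The 43 is copied from the EVRL study's intended enrolment.

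**Inputs.** From the documents: 43 GVL subjects, EVRL success 75%, threshold 70%, level 0.05. Assumed: 43 EVRL subjects analysed (the number is not given), two-sided test, VAS change roughly normal with equal SD.

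**Step 1: what can be non-significant.** The critical t with 84 df is 1.989. The 95% CI half-width is 1.989 × √(2/43) = 0.429 SD, so any smaller observed difference gives p≥0.05. For assumed SDs of 15, 20, 25 and 30 mm this is 6.4, 8.6, 10.7 and 12.9 mm.

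**Step 2: t-test alone.** A drop in true success from 75% to p is a shift of z(0.75) − z(p) SD. Power comes from the noncentral t with noncentrality shift × √(43/2).

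| True GVL success | Shift (SD) | Power | P(non-significant) |
|---|---|---|---|
| 70% | 0.674 − 0.524 = 0.150 | 0.106 | 0.894 |
| 65% | 0.289 | 0.263 | 0.737 |
| 60% | 0.421 | 0.488 | 0.512 |

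With 40 or 44 EVRL subjects the 65% row is 0.745 or 0.734.

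**Step 3: add the 70% rule.** 0.70 × 43 = 30.1, so at least 31 successes are needed (30/43 = 69.8%). The binomial chance of that is 46%, 21% and 7% at true success of 70%, 65% and 60%.

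The rule and the t-test use the same GVL subjects, so their joint chance was simulated with 20,000 trials per setting. Baseline was uniform on 50–90. Percent decrease was normal with SD 20–40, capped at 100%, and centred so that the chance of a 30% decrease equals the stated success rate. The t-test was run on mm change.

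| True GVL success | Rule met | Rule met and t-test non-significant | Non-significant, given rule met |
|---|---|---|---|
| 70% | 46% | about 44% | about 96% |
| 65% | 21% | 19–20% | about 94–95% |
| 60% | 7% | about 6% | about 88–90% |

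The conditional figures in the lower rows carry simulation error of a point or two, because few trials pass the rule. In the same simulation the t-test alone was non-significant in 90%, 75–77% and 54–56% of trials, close to Step 2.

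**Step 4: what a margin would need.** If the devices are truly equal, 80% power to exclude a loss at 43 per group needs a margin of about 0.611 SD, or 9.2, 12.2, 15.3 and 18.3 mm for SDs of 15, 20, 25 and 30.

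**Step 5: proportions.** With both at 75%, the 95% CI half-width for the difference is 1.96 × √(2 × 0.75 × 0.25/43) = 0.183, about 18 points against a 5-point margin.

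**The case against.** The strongest reply is that the t-test is only supportive. It does not enter the 70% rule, so nothing about pass or fail changes. That stands, and it is why the point is minor.

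The plan also never says that p≥0.05 will be read as equivalence. That is true, and the reading is an inference. But if it is rejected, the analysis has a stated purpose and no criterion at all, so the text needs repair either way.

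A reader might infer from the 89% and 74% figures that the trial would usually be reported as showing supported equivalence even if GVL were worse by the plan's margin or twice that margin. The documents do not support this. The t-test can support a conclusion only where the 70% rule is met, and at 65% true success about four trials in five fail that rule. The joint figures, 44% and 19–20%, are the relevant ones. What survives is that among passing trials the t-test almost never dissents.

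A reader might also infer that EVRL results play no part in the primary rule. They do: the observed 75% fixes the threshold. Only its uncertainty is left out.

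Finally, the red-only bullet might be taken for a second planned comparison with missing data. The next bullet names the right groups, and Blinding fixes the two data sets. The plan identifies red-only EVRL as the reference for the preceding EVRL study, so leftover wording is the likely explanation, though that too is inference. It is a clerical matter.

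**Conclusion.** The concern holds and is minor. As written, the Change Scores test cannot provide the support for equivalence that the SAP assigns to it, because it is a difference test with no VAS margin and no interval rule. Once the 70% rule is met, a non-significant result is close to automatic across true GVL success rates from 70% down to 60%, so reporting it as corroboration would overstate the evidence. Comparison of Proportions has the same structure and the same weakness, although a margin for it is already stated.

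The figures rest on 43 analysed EVRL subjects, a two-sided test, true EVRL success of 75% and roughly normal change. The mm values also rest on assumed SDs. The logical point depends on none of these.

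**What to change.** Replace both Change Scores bullets with one: the GVL minus red/violet EVRL difference in mean VAS change from baseline to endpoint, with a two-sided 95% CI, in the ITT and PP populations. Then choose one of two routes:

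- State and justify a VAS non-inferiority margin before the GVL data are analysed, and call the result supportive only if the CI excludes a loss larger than that margin.
- If no margin can be justified, report the estimate and CI descriptively, and remove the equivalency wording and the p<0.05 criterion from this section.

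Repair Comparison of Proportions in the same way, reporting the CI for the difference in success proportions against the stated 5-point margin. Deleting the red-only bullet is part of the same edit.

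The cost is a few lines of SAP text and, on the first route, a short margin justification. No subjects, visits or data are added, and the 70% rule stays as it is. The drawback is that the intervals are wide at this sample size: about ±0.43 SD for VAS change, and about ±18 points for the proportions if both are near 75%. The supportive results may therefore be inconclusive, and the report should then say so.
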